8.0 PARTICIPANT MANAGEMENT

8.1 Participant Retention

We will collect multiple forms of participant contact information and study-related communication preferences (e.g. email, phone/text, social media handles) as part of study enrollment. The HMP app supports participant retention through a timeline that displays upcoming study activities and a two-way secure messaging feature for participants and study staff. The study staff-facing web-based administrative portal also facilitates retention via prompts to reach out to participants who have missed specified study activities and by providing a secure platform to communicate with participants and deliver participant incentives. The study team will meet weekly

and review retention reports and proactively identify barriers to retention.

8.2 Participant Remuneration

Participants will receive remuneration throughout the course of their participation. Intervention and control arm participants are eligible to receive the same level of remuneration.

- Participant enrollment activities: \$60
- Participant follow-up 3-month survey: \$40
- Participant follow-up 6-month survey: \$40
- Participant follow-up 12-month survey: \$40
- Participant return of 3-month whole blood self-collection kit: \$50
- Participant return of 6-month whole blood self-collection kit: \$50
- Participant qualitative exit interview (sub-sample of participants): \$50
- Clinician/Stakeholder/Staff qualitative interview and brief survey: \$50

8.3 Suspected or Confirmed HIV/STI Infection at Screening, or While on Study

Individuals who self-report a prior HIV diagnosis or reactive HIV test at screening will not be eligible for the study. Once participants have completed informed consent and a HIPAA waiver, HIV status can be confirmed by study staff (access to lab results via state or clinic portals). If lab results are not available, participants/clinics may use a secure link to self-report a recent (<90 days) test result to confirm HIV negative status.

Individuals who are found to be HIV seropositive at time of eligibility verification will not complete enrollment. Participants who test positive for HIV or other STIs at any point during study follow-up will be appropriately connected to care through the North Carolina State Health Department's standard notification procedures and Disease Intervention Specialists.⁴⁵ All participants are encouraged to adhere to CDC recommended frequency of testing which includes screening for bacterial STIs every 3 months among MSM or among patients with ongoing risk behaviors³¹. Therefore, HIV/STI testing will be completed as part of patients' routine care at established STI clinics (not administered through the study). The HMP app and study staff will help facilitate participants' return to STI clinics for HIV/STI testing by providing in-app appointment reminders, text messages and phone calls, as needed. Test results will be communicated to participants by clinic staff following their standard of care and established notification procedures. Study staff will not communicate HIV/STI test results to participants directly. The conduct of HIV/STI testing at 3 & 6 months is considered routine clinical care.

For patients who initiate PrEP, quarterly HIV and STI testing will be ordered by the prescribing PrEP provider, at their clinical discretion. These participants may not require additional HIV or STI testing (see Section 6.3). Post-hoc abstraction of HIV/STI test results by research staff is considered a research activity and is covered by the HIPAA authorization form participants sign at study enrollment. Participants who initiate PrEP will have HIV/STI testing results abstracted from HD (if HD-based PrEP) or external PrEP providers' records, or, if access to such records is not feasible, participants will be asked to upload the results of said testing within the app portal. Participants who receive an HIV diagnosis while enrolled in the study will be study stopped. Following an HIV seroconversion SOP, study staff will document that the participant has been notified and received appropriate counseling as described above. Participants will have an opportunity to complete an end-of-study survey to capture any interim PrEP use and referral for or initiation of HIV treatment. A seroconversion CRF will be completed for any such participants and indication noted in the HMP study staff-facing administrative portal for study staff and PrEP navigators. Participants who test positive for other STIs will continue to be eligible for study participation.

8.4 Participant Withdrawal

Enrolled participants are free to withdraw from participation in the study at any time and for any reason upon request. A study stop CRF will be completed for participants who request withdraw from the study. No further data collection will occur following completion of the study stop CRF.

An investigator may withdraw a participant from the study for the following reasons:

- a) If any clinical adverse event (AE), serious adverse event (SAE), laboratory abnormality, or other medical condition or situation – related or unrelated to the study – develops after enrollment such that continued participation in the study would not be in the best interest of the participant.
- b) If a patient presents a safety risk to the research staff.
- c) If their participation in the study is disruptive to the study or the clinic.
- d) If the participant receives an HIV diagnosis (see section 8.3).
- e) They intentionally violate study procedures, including fraudulent engagement with study screening or DHI-based survey completion.

The reason for any participant's discontinuation or withdrawal from the study will be recorded on the study stop CRF.

Furthermore, study staff may use their professional discretion not to enroll a prospective participant for reasons b through e, listed above.

9.0 STATISTICAL/ANALYTIC CONSIDERATIONS

9.1 Sample Size and Power Estimate

We expect > 7,400 patients will present for care in the 21-month enrollment period, with 20-35% study eligible. Aim 1 analysis includes eligible, consenting patients who successfully download the HMP app. The study will enroll for 21 months with a target sample size of 336. We expect approximately half of participants will be randomly assigned to the intervention arm and the remaining half to the control arm (see Randomization, Section 3.2).

We calculated statistical power for the effect of intervention upon PrEP uptake by 3-month follow-up using SAS 9.4 (Cary, NC) with a 5% type I error rate and a two-sided Chi-square test. Assuming 2.5% of eligible patients start PrEP within 3 months in the control arm, we calculated statistical power to detect a range of small to large effect sizes from 5% to 15% percentage point increases in PrEP uptake under a range of possible sample sizes and assuming 10% missing data (Table 4). At a total sample size of 336, given our design and assumptions, we will have >88% statistical power to detect medium (10%) and large (15%) effect sizes, and 80% statistical power to detect a moderate (7.5%) effect size.

Effect size rationale: As there is currently limited-to-no infrastructure or existing programming providing PrEP in rural North Carolina STI clinics, no prior studies that we are aware of have measured PrEP uptake in these settings. Overall, U.S. PrEP coverage of those assigned male sex at birth with PrEP indications was reported by CDC as 18.4% in January – March 2021, but only 5.6% among Black/African American⁴⁶, who will constitute a large portion of our sample. Among the CDC-designated End-the-Epidemic jurisdictions, recent PrEP coverage estimates of those with PrEP indications range from a low of 4.5% in San Bernardino to a high of 42.3% in San Francisco; North Carolina's state level PrEP coverage estimate is 13.3%, which belies the wide variability from

urban to rural areas⁴⁷. Looking to other settings with some comparable characteristics, the THRIVE national CDC demonstration project (n=9538 PrEP-eligible MSM) found a range across study sites of 10.7% to 95.9% (mean 53.8%) of eligible screened participants linked to PrEP services (defined as attending an initial PrEP appointment), with substantially fewer being prescribed PrEP (37.2%). At sites where PrEP navigation was provided, **48.5% of MSM who used navigation were linked to PrEP as compared to 2.8% being linked among those who did not use navigation** ⁴². In a pilot RCT mHealth app (**without navigation**), overall PrEP uptake among a primarily urban MSM population was 12.8% overall (n=6/58) with no difference between intervention and control arms⁴⁸. Among an urban sample of 2106 PrEP-priority eligible MSM attending sexual health clinics in New York City who were offered PrEP navigation services, 288 (13.6%) linked to a PrEP provider and 235 (11.2%) received a PrEP prescription⁴⁹. Looking at these data together and considering the added barriers posed by our rural setting and PrEP stigma, we anticipate being able to see a moderate effect size and have conservatively selected a preliminary intervention efficacy milestone of an observed difference in PrEP uptake of at least 7.5% (see Table 6). This conservative, but still clinically meaningful, effect size will be used as part of the overall determination of whether the intervention approach should be explored further in Phase 2 (see 11.0 Milestones for further discussion).

Based on historical testing data, we expect <2% of all persons who are undergoing HIV screening on day of enrollment to be seropositive. Persons with unidentified HIV at time of enrollment should be randomly distributed between the intervention and control groups. Given the small proportion we anticipate may be enrolled/randomized prior to seropositive results being available, our study remains powered to detect the differences as described above.

Table 4: Statistical power as a function of the observed difference in effect (PrEP uptake) and sample size*

| TOTAL SAMPLE SIZE – R61 PHASE | | | | | |
|------------------------------------|-------|------------|-------|-------|-------|
| OBSERVED DIFFERENCE IN PREP UPTAKE | n=200 | n=300 | n=400 | n=500 | n=600 |
| 5% | 33% | 47% | 58% | 68% | 76% |
| 7.5% | 59% | 77% | 87% | 93% | 96% |
| 10% | 72% | 88% | 95% | 98% | 99% |
| 15% | 92% | 98% | 99% | >99% | >99% |

*Assuming PrEP uptake of 2.5% in the control arm, 10% missing data at month 3, and 5% type I error

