| SAMPLE SIZE: | Phase 1 Intervention trial: 336 STI clinic patients across all participating clinics. Implementation evaluation: up to 50 clinic staff, providers and other key stakeholders. |
| POPULATION: | Intervention trial participants enrolled who will contribute to final study outcomes will be HIV-negative individuals who were assigned male sex at birth or cisgender women, are not currently using PrEP at enrollment, have regular access to a smartphone, aged 18 to 39 years who report sexual activity with a male in the past 12 months and are presenting for STI testing or care to participating clinics and/or clinic events in North Carolina. |

| | |
|--------------------|---|
| RECRUITMENT SITES: | Rural and peri-urban NC STI clinics. |
| STRATIFICATION: | Intervention trial participants will be randomized 1:1 to the control or intervention condition at enrollment using blocked randomization stratified by county, with randomly ordered blocks of sizes 4 and 6. |
| DATA COLLECTION: | 
Data sources:
 
 - Computer assisted self-interviewing (CASI) biobehavioral surveys - STI/HIV test results - Dried Blood Spots (DBS) to detect PrEP use - Medical records related to PrEP initiation and care - Daily app use data collected automatically by the DHI app's analytic system and as entered by participants - Process data measures collected from study implementation records - Qualitative in-depth interviews (IDI) with a subsample of up to 50 intervention trial participants and up to 50 clinic staff/providers/key stakeholders - Direct observations (time-and-motion) and relevant invoices/receipts for costing 
Data collection points:
 
Baseline, 3-months, 6-months (subset), 12-months (subset).
 
Participants enrolled in approximately the final quarter of enrollment will only complete baseline and 3-month data collection points.
 
Daily app use, PrEP adherence tracking, and behavioral tracking. Costing data collection will be embedded into daily study activities.
 |

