5.8 Participant Randomization

Participants will be randomized 1:1. Randomization procedures are automated through the study database. Randomization is completed after a participant has completed informed consent and their Baseline survey. Participants will be informed by study staff of their study condition assignment during their onboarding appointment. The study onboarding appointment is tailored to the study arm condition they are assigned (Figure 2).

Study staff are trained to follow similar protocol for scheduling, enrollment, and follow-up regardless of arm which includes the use of IRB-approved guides for participant communications and specified standard operating procedures for participant outreach mode, timing, and frequency. Communication attempts will be tracked in a communication log for prospective and enrolled persons. PIs and the study monitor will be able to see the records for all those who complete screening and could assess whether there is differential communication efforts or enrollment by randomization condition.

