6.1 Study onboarding appointment and baseline assessment

[figure not shown]
All participants will complete an onboarding appointment via phone or HIPAA-compliant videoconferencing platform. Participants will be considered enrolled and be eligible for the enrollment completion incentive once the below activities are complete:

- Informed consent and HIPAA authorization. Receipt of a unique access link to complete their Baseline CASI survey capturing PrEP use history, sexual behaviors, demographics, and determinants of PrEP use (access to care, perceived HIV risk, social support, perceived discrimination, mental health, substance use, and PrEP decision making). The CASI survey is self-administered via secure HIPAA-compliant platform (e.g. RedCap) and participants can complete the survey on their personal device with internet, wi-fi or mobile data. The survey saves after every page thus participants can return to complete the survey if their connection is disrupted or for any other reason.
- Randomized to study condition.
- Receipt of a unique access code and directions to download their free designated version (intervention or control) of the HMP study app from either the Google Play or Apple store.
- Creating their unique HMP account profile and log-in; touring the app features.

The onboarding appointment for intervention participants will also include being connected to their assigned PrEP navigator.

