9.2.1 Primary Outcome Analyses

The primary outcome of PrEP uptake is measured at the 3-month follow-up. The effectiveness of the intervention will be estimated as the difference in proportion of participants starting PrEP within 3 months of an index STI clinic visit, comparing patients randomized to the intervention and control groups. For participants enrolled through clinic-collaborating outreach events, the date of clinic outreach serves as the index visit.

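### Section 9.1 limits the Aim 1 analysis to app downloaders, a step after randomisation; 9.2.1 sets no such condition, and randomised non-downloaders are not covered

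*Combined protocol and SAP*

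**What the plan says.** **Who is analysed.** Section 9.1 says "Aim 1 analysis includes eligible, consenting patients who successfully download the HMP app". Section 9.2.1 describes the primary estimate as a difference in proportions, "comparing patients randomized to the intervention and control groups", and does not mention the app. The Study Synopsis (Population) gives a third description: "Intervention trial participants enrolled who will contribute to final study outcomes will be HIV-negative individuals".

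**When download happens.** Section 5.8: "Randomization is completed after a participant has completed informed consent and their Baseline survey". Section 6.4 instead places randomisation at the point where the participant connects with staff for onboarding. Section 6.1 lists, after randomisation, "Receipt of a unique access code and directions to download their free designated version (intervention or control) of the HMP study app", followed by creation of an app account. Table 2.2 puts app account generation under the post-randomisation heading, on day 0.

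**Who counts as enrolled.** Section 6.1: "Participants will be considered enrolled and be eligible for the enrollment completion incentive once the below activities are complete". The list that follows includes randomisation and account creation.

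**What differs by arm.** Section 5.8: "The study onboarding appointment is tailored to the study arm condition they are assigned". Section 6.1: "The onboarding appointment for intervention participants will also include being connected to their assigned PrEP navigator".

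No section names an intention-to-treat set or any other analysis set. Section 9.2 deals with missing values and baseline imbalance in general terms only.

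**The concern.** Two sections give different denominators for the primary outcome. The one in 9.1 depends on something participants do after they have been assigned to an arm and may already know which arm it is. If those who fall away before download differ between arms in number or in readiness to start PrEP, the remaining groups are no longer the randomised groups. A difference in uptake could then partly reflect who was dropped.

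The same comparison decides milestone 5, which section 11.0 makes a required Go/No-Go criterion, and it feeds the incremental cost per PrEP start in section 10.4. With the denominator open, the choice could also be made after outcomes by arm are known.

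**Working it through.** **1. The plan's own figure.** Inputs from section 9.1: 336 participants (168 per arm), control uptake 2.5%, difference 7.5 points, two-sided 5% chi-square test, 10% missing (about 151 evaluable per arm). The stated power is 80%. The pooled normal formula gives 81.3% with 168 per arm and 77.1% after the 10% loss. Exact enumeration of the chi-square test with 151 per arm gives 79.7%. The stated figure is reproduced closely enough, and the point below does not depend on it.

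**2. Is download after assignment?** Yes. The app version is arm-specific (6.1), randomisation precedes the access code in the 6.1 list, and account generation is a post-randomisation activity (Table 2.2).

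**3. Does reading 9.1 as the enrolled set help?** No. Under 6.1 a person is enrolled only after randomisation and account creation, so that set is also fixed after assignment.

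**4. How large could the effect be?** No non-download rate is documented, so the rates below are assumptions. Take no true effect, uptake *u* in both arms, and non-downloaders who never start PrEP. Uptake among downloaders is then *u* divided by the download rate.

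At *u* = 2.5%, control download of 95% gives 2.5/0.95 = 2.63%. At *u* = 5%, it gives 5/0.95 = 5.26%. Error rates come from 1,000,000 simulated null trials per scenario (168 per arm, 10% missing, Pearson chi-square at 5%).

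| *u* | Download, intervention vs control | Downloader uptake | Shift (points) | Two-sided error | Error favouring intervention |
|---|---|---|---|---|---|
| 2.5% | 95% vs 95% | 2.63% vs 2.63% | 0 | 4.8% | 2.4% |
| 2.5% | 90% vs 95% | 2.78% vs 2.63% | +0.15 | 4.9% | 3.0% |
| 2.5% | 85% vs 95% | 2.94% vs 2.63% | +0.31 | 5.1% | 3.5% |
| 2.5% | 80% vs 95% | 3.13% vs 2.63% | +0.49 | 5.4% | 4.2% |
| 5% | 90% vs 95% | 5.56% vs 5.26% | +0.29 | 5.1% | 3.2% |
| 5% | 85% vs 95% | 5.88% vs 5.26% | +0.62 | 5.6% | 4.2% |
| 5% | 80% vs 95% | 6.25% vs 5.26% | +0.99 | 6.4% | 5.4% |

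With all randomised participants analysed, two-sided error is 4.7–4.8% at 2.5% uptake and 4.9% at 5%. Error favouring the intervention is 2.4% and 2.5%. Reversing the rates reverses the sign: at 95% vs 80% and 2.5% uptake, two-sided error is again 5.4% and error favouring the intervention falls to 1.2%. If non-downloaders start PrEP as often as downloaders, the shift is 0.

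**5. Scale.** The 95% CI half-width at 2.5% uptake is 1.96 × √(2 × 0.025 × 0.975 / 151.2) = 3.5 points. A 1-point false shift at 2.5% uptake would need intervention download of 2.5/(2.632 + 1) = 68.8%, against 95% in control.

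**6. Equal loss in both arms.** There is no bias under the null, but the quantity estimated changes. If non-downloaders never start, a 7.5-point difference among all randomised reads as 7.5/0.95 = 7.9 points at 95% download and 7.5/0.90 = 8.3 at 90%.

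**The case against.** The 9.1 sentence sits in a paragraph about accrual, while the section that specifies the primary comparison already compares patients as randomised. Sections 5.8 and 6.4 can be reconciled: consent, survey, connection with staff, then randomisation. Account generation is scheduled for day 0, so non-downloaders would be people lost within one staff-led appointment. Figure 2 and the trial schema, not available in the text read here, may settle the order. Section 5.8 also requires similar scheduling, enrollment and follow-up procedures in both arms, with a communication log. Its remark on differential enrollment is a monitoring step and is not evidence that a difference is expected. The illustrated shifts need arm gaps of 5 to 15 points and zero uptake in every non-downloader.

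The remedy has limits as well. If every never-onboarded participant lacks an outcome, a complete-case analysis of all randomised equals the downloader analysis. Weighting or imputation helps only as far as measured data explain the missingness. Power also falls somewhat: with 10% uptake in intervention downloaders, 2.5% in everyone else, and 10% missing, it is 74% or 71% for all randomised at 5% or 10% non-download, against 75% or 73% in downloaders.

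Most of this stands as a limit on the weight of the point. It does not remove the conflict. The 9.1 sentence says what the analysis includes. Section 13.4 repeats the rule for the primary analysis of the R33 phase, although that phase is not randomised and the repetition is only supporting evidence. Section 9.2.4 treats successful installation as something to be measured, so the plan does not take it for granted.

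**Conclusion.** The point holds. Section 9.1 conditions the Aim 1 analysis on a post-randomisation step, 9.2.1 does not, and nothing in the plan covers randomised non-downloaders. Size and direction are unknown because no download rate is given. Under the assumed rates the false difference is 0.15 to 0.49 points at the plan's 2.5% uptake and 0.29 to 0.99 points at 5%. Both ranges are well inside the confidence interval half-width and the 7.5-point milestone. Exposure is probably small if randomisation occurs at onboarding, and larger if it can occur earlier, after the baseline survey. This should be fixed because the comparison carries the Go/No-Go decision and the remedy is cheap. On these figures it does not threaten the trial.

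**What to change.** Replace the 9.1 sentence with: *The primary Aim 1 analysis includes all eligible randomised participants in the arm assigned, whether or not they completed onboarding or downloaded the app.* Keep the existing HIV-negative eligibility rule, applied identically in both arms. Report non-download by arm, and retain the downloader set as a labelled sensitivity analysis. Align the timing of randomisation in 5.8 and 6.4 and the enrollment definition in 6.1. Settle all of this before outcomes are compared by arm.

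The cost is one replaced sentence, aligned wording in three sections, and no new instrument. Randomisation is automated in the study database (5.8), so randomised non-downloaders can be listed. Their outcomes can be sought without the app through the web survey, the mailed DBS kit, record abstraction under the HIPAA release, and email, phone or SMS contact. At the section 8.2 rates, the 3-month survey and kit payments come to $40 + $50 = $90 per additional person followed, plus kit and laboratory costs that the plan does not state. Some never-onboarded participants will still have missing outcomes. These fall to the weighting or imputation already foreseen in 9.2, which can draw on the baseline survey that 5.8 requires before randomisation.

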11.0 MILESTONES

Milestones are summarized and defined in Table 6. Specific Go/No-Go criteria for proceeding to the R33 phase include the study meets or exceeds the two effectiveness outcome milestones (milestones #5 and 6 in Table 6), and at least four of the six R61 milestones, overall. Due to changes in the study design since initial Notice of Award, including expanding the number of involved sites and revising study design from a cluster randomized trial at the clinic level to a participant-randomized trial, some milestones have been adjusted or adapted to accommodate these differences. Revisions have been incorporated where the original wording is no longer applicable or aligned with the current design. Functionally, these still represent criteria that capture critical administrative, implementation, and effectiveness outcomes which inform decisions regarding proceeding to the next proposed phase of study (R33).

As noted in section 9.0, the study is designed to have adequate statistical power to detect an improvement in PrEP initiation at 3 months of 7.5 percentage points between the intervention arm and control arm. A statistically significant improvement would meet milestone 5. Any other scenarios would be at the discretion of NIH. For milestone 6 (see Table 6), the milestone will be met if at least 50% of those who initiate PrEP sustain

PrEP use for ≥3 months as manifest by follow-up PrEP prescription or ongoing engagement in PrEP care. Any other scenario would be at the discretion of NIH.

For milestone 5, if a statistically significant improvement is not achieved, we will explore whether the intervention is still worth pursuing at the R33 phase with further refinement and development by examining whether there are subgroups (of clients and/or clinics) for which the intervention may be effective. We propose examining the following as part of this assessment, and exploring whether there are revisions that would be worthwhile and feasible to pursue:

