| Y3 (end of trial) | (6) Among intervention arm PrEP initiators, ≥50% sustain use ≥3 months | Among participants in the intervention arm who have initiated PrEP and for whom 3-months of study follow-up time has elapsed since PrEP initiation, at least 50% will sustain PrEP use for ≥3 months as indicated by engagement in PrEP care (on-time visits/refills/injections) and self-reported PrEP use. Any other scenarios would be at the discretion of NIH. We will also report the number of participants who initiate PrEP after their 3-month study visit and thus have less than 3-months of available PrEP sustainment data at their 6-month follow-up visit. |
| R33 | | |
| | Established relationship with HD stakeholders and letters of support | |
| | Refined strategy approved by key stakeholders for implementation | |

| | | |
|--|--|--|
| | Interactive costing interface platform finalized | |
| | Refined strategy $\geq 75\%$ effective (PrEP uptake) vs R61 intervention | |

^a Year 1 refers to the RCT pre-implementation phase aligning with the grant timeline (Budget Period 1: June 13, 2022 – May 31, 2023).

^b Because participants for whom intended follow-up is limited to 3-month outcomes are scheduled to have only 1 DBS, criteria for these participants is as follows: $\geq 50\%$ have completed the 3-month survey, and $\geq 50\%$ have returned 1 DBS. Any other scenarios would be at the discretion of NIH.

^c The original grant proposal specified this milestone as pertaining to PrEP uptake at a clinic level compared to "pre-intervention baseline". However, this is not applicable because revisions to the study now specify randomization will be at the individual (rather than clinic) level with comparison of intervention versus a concurrent control arm. This change describes the effect of the intervention above background uptake in the control arm during the same time (e.g., to control for secular trend). Power analysis suggests that this milestone will reach statistical significance at a 7.5% difference, as clarified in the definition.

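### The 7.5-point row of Table 4, and the 80% power quoted at N=336, are not on the same basis as the other three rows; by the method that reproduces those rows, power at N=336 is about 77%

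*Combined protocol and SAP*

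**What the plan says.** Section 9.1 calculates power for 3-month PrEP uptake "with a 5% type I error rate and a two-sided Chi-square test", takes control uptake as 2.5%, and covers increases of 5 to 15 points "under a range of possible sample sizes and assuming 10% missing data (Table 4"). The Table 4 footnote repeats the control rate and adds "10% missing data at month 3, and 5% type I error". Nothing sets a separate basis for any row.

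At the target of 336 the text claims "80% statistical power to detect a moderate (7.5%) effect size" and more than 88% for 10 and 15 points. Table 4 has no n=336 column. Its 7.5-point row, for n=200 to 600, reads "7.5% | 59% | 77% | 87% | 93% | 96"%, and its 10-point row reads "10% | 72% | 88% | 95% | 98% | 99"%.

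The 7.5-point figure is used again in section 11.0, which says that "the study is designed to have adequate statistical power to detect an improvement in PrEP initiation at 3 months of 7.5 percentage points", and in Table 6 footnote c: "Power analysis suggests that this milestone will reach statistical significance at a 7.5% difference".

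**The concern.** The steps down the n=200 column of Table 4 are uneven. Power goes from 33% to 59% to 72% as the difference goes from 5 to 7.5 to 10 points, so the two equal steps in effect add 26 and then 13 points. On the basis that fits the 5- and 10-point cells, the same steps add 21.2 and 17.7 points. The middle row looks too high for its neighbours.

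That row matters most. A difference of 7.5 points is the milestone 5 effect size and the only one for which the text claims 80% power. If milestone 5 is missed, the next step goes to NIH discretion and subgroup exploration, and readers are likely to use the stated power when they judge a non-significant result.

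**Working it through.** **Inputs (section 9.1, section 5.8 and the Table 4 footnote).** Two-sided α = 0.05, so z = 1.96; control rate p0 = 0.025; intervention rate p1 = p0 + difference; 1:1 allocation; 10% missing, so n per arm = 0.9 × N / 2.

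**Formula (pooled-variance chi-square approximation).** With p̄ = (p0 + p1)/2,

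power = Φ{ [√n · (p1 − p0) − 1.96 · √(2p̄(1 − p̄))] / √[p0(1 − p0) + p1(1 − p1)] }.

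**Step 1: reproduce the table.**

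| Difference | Source | n=200 | 300 | 400 | 500 | 600 |
|---|---|---|---|---|---|---|
| 5 | printed | 33 | 47 | 58 | 68 | 76 |
| 5 | formula | 33.6 | 47.0 | 58.6 | 68.3 | 76.1 |
| 10 | printed | 72 | 88 | 95 | 98 | 99 |
| 10 | formula | 72.5 | 88.1 | 95.3 | 98.2 | 99.4 |
| 15 | printed | 92 | 98 | 99 | >99 | >99 |
| 15 | formula | 92.5 | 98.7 | 99.8 | >99 | >99 |
| **7.5** | **printed** | **59** | **77** | **87** | **93** | **96** |
| **7.5** | **formula** | **54.8** | **72.3** | **83.9** | **91.0** | **95.2** |

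Three rows agree within 1 point in all 15 cells. The 7.5-point row is high in every cell, by 4.2, 4.7, 3.1, 2.0 and 0.8 points.

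**Step 2: the target sample size.** n per arm = 336 × 0.9 / 2 = 151.2; p1 = 0.10; p̄ = 0.0625.

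- √151.2 × 0.075 = 0.9222
- 1.96 × √(2 × 0.0625 × 0.9375) = 0.6709
- √(0.024375 + 0.09) = 0.3382
- (0.9222 − 0.6709)/0.3382 = 0.743, and Φ(0.743) = 77.1%

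The printed 80% agrees with the printed row: linear interpolation between n=300 and n=400 gives 77 + 0.36 × 10 = 80.6%. The text and the row therefore share the discrepancy. For 5, 10 and 15 points the formula gives 51.4%, 91.4% and 99.3% at N=336, so the claim of more than 88% for the two larger effects holds.

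**Step 3: what would fit the 7.5-point row.** Three explanations match it within 1 point:

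| Explanation | 7.5-point row, n=200 to 600 | N=336 |
|---|---|---|
| Same formula, no missing-data allowance | 59.2/76.8/87.5/93.6/96.8 | 81.3 |
| Arcsine approximation, 10% missing | 59.0/76.4/87.1/93.3/96.6 | 80.9 |
| Same formula, 10% missing, 8.0 points entered | 58.7/76.3/87.2/93.3/96.7 | 80.9 |

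Each requires this row to have been run differently from the others. Without the allowance, the 5-point row would be 36.7/51.1/63.2/72.9/80.4. By arcsine, the 10-point row would be 77.6/91.4/97.0/99.0/99.7. Neither is what is printed.

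**Step 4: other methods with 10% missing.** The unpooled formula gives 55.7% at n=200 and 77.8% at N=336 for 7.5 points. Exact enumeration of the Pearson test (90/135/180/225/270 per arm, and 151 for N=336) gives:

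| Difference | n=200 | 300 | 400 | 500 | 600 | 336 |
|---|---|---|---|---|---|---|
| 5 | 31.1 | 47.6 | 60.1 | 70.0 | 78.1 | 52.4 |
| 7.5 | 55.1 | 75.2 | 86.5 | 92.9 | 96.6 | 79.7 |
| 10 | 75.6 | 91.1 | 96.9 | 99.0 | 99.7 | 93.6 |

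This supports about 80% at N=336, but it departs from the printed 59% (7.5 points) and 72% (10 points) at n=200. None of the pooled, unpooled, arcsine or exact calculations, with or without the 10% allowance, fits all four rows.

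**Step 5: size in other units.** By the pooled formula, 336 enrolled gives 80% power at a difference of 7.88 points. For 7.5 points, 80% needs 163 evaluable per arm, 326 in total, or 326/0.9 = 363 enrolled after rounding up.

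**The case against.** The plan names the chi-square test but not the approximation used for its power. Exact power of that test at 151 per arm is 79.7%, which rounds to the printed 80%; a likelihood-ratio version gives 79.4% and arcsine 80.9%. On this view the headline sentence is about right, and replacing it with 77% would move it away from the exact value, because the pooled formula understates exact power here. The 15-point row also barely separates the methods, so the match to 15 cells rests on fewer informative ones. Finally, milestone 5 turns on the observed result and its significance, and a null result would be read mainly from the confidence interval promised in section 9.2.

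Much of this stands. The trial has not been shown to be underpowered for its target, and 77% should not be presented as its one true power. The practical effect is small, also beside the uncertainty in the 2.5% control rate, since section 9.1 knows of no earlier study of uptake in such clinics. The objection does not rescue the table. Defending 80% by exact enumeration means changing the 10-point row and the n=200 cell of the 7.5-point row; keeping the other rows means lowering the 7.5-point row and the 80%.

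**Conclusion.** The concern holds. Under the assumptions stated for the whole of Table 4, the 7.5-point row is on a different basis from the other three, and the method that reproduces those three gives 77.1% at N=336. The row is high by up to 4.7 points on that method. At N=336 the shortfall from 80% is about 0 to 3 points: 77.1% pooled, 79.7% exact, and none by arcsine (80.9%). By the exact method the printed row is clearly off only at n=200 and lies within about 2 points from n=300 upward. These figures assume 2.5% control uptake, equal arms and 10% loss in each arm. The cause cannot be settled from the documents. It is a reporting error that should be fixed, not a design fault.

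**What to change.** Recompute all of Table 4 by one named method with 10% missing in every row, add an n=336 column, and make section 9.1 match. Check the statements in section 11.0 and Table 6 footnote c against the result. Either choice is defensible:

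- **Option A, the method behind the other three rows.** 7.5-point row 55/72/84/91/95%; n=336 column 51/77/91/99% for 5/7.5/10/15 points. The text would state about 77% power for 7.5 points, with 80% reached at about 7.9 points.
- **Option B, exact enumeration of the Pearson test.** 7.5-point row 55.1/75.2/86.5/92.9/96.6%; n=336 column 52.4/79.7/93.6/99.7%. The text may keep about 80%, but the other rows change too; for example, the 10-point row becomes 75.6/91.1/96.9/99.0/99.7%.

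Option B is closer to the true power of the named test, and Option A changes fewer cells. The cost is a table and text correction. Stated power falls by about 3 points under A and stays at about 80% under B. Enrolment need not change.
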